HV3 (between weeks 6-11)	
CHW inquires how patient and family are doing. Review care coordination, action plan, goals, medications, and relevant community resources.
 
Review use of tablet and PP:
 
 • Problems with use addressed • Complete at least 2 tasks with PP • Show how to email if not known already 	Email/phone to patient encouraging sign in to PP.
DC-week 12	Participant called by a member of the research team for data collection.	

Table 1 (continued). Activities and data collection (DC) for PT+HV and PT groups.

Time	PT+HV	PT
HV4 (between weeks 23-27)	CHW inquires how patient and family are doing. Review care coordination, action plan, goals, medications, and relevant community resources. Review use of tablet and PP: 
 • Problems with use addressed • Review how to “google”, email, and how to get weather and latest news on the internet 	Email/phone to patient encouraging sign in to PP.
DC – week 28	Participant meets with a data collector for data collection which includes spirometry.	
DC-week 36	Participant called by a member of the research team for data collection.	
DC week 48-50	Participant meets with a data collector for data collection which includes spirometry.	
DC every 12 weeks	Participant called by a member of the research team for data collection.	

CHW= community health worker, DC= data collection, PP= patient portal, PT= patient portal training, PT+HV= patient portal training plus home visits, HV1= first home visit, etc.

Patient Portal Training (PT)

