(2) "Exclusion restriction". The effect of the assignment to the home visitor arm of the study must influence outcome only through the actual completion of the home visit. A patient would have to react the same in terms of asthma outcome if he or she had been assigned to the home visitor treatment arm or the portal only arm, and had received no home visits. In the context of this study, this key assumption would be violated if the mere assignment to the home visitor led to higher expectations of improved asthma outcome just by learning of the assignment, and diminished expectations upon learning of assignment to the patient portal arm. Owing to the unavoidable fact that the patients could not be blinded to the treatment assignment, a violation of this assumption might be possible. But it might be that both the home-visitor patients and the portal-only patients could have similar expectations of some improvement merely by being recruited to the study and followed over time. A variation on this assumption requires that the patient who is randomized to the home visitor group but who does not schedule or see the home visitor (lack of compliance with the protocol) will receive no benefit from just being assigned to the home visit group. That assumption seems plausible in this setting.

(3) The final assumption, "monotonicity", requires that patients assigned to the portal group did not obtain home visits. Our design satisfied this assumption because only patients assigned to the home visit arm of the study were able to receive home visits. Although this assumption was very likely satisfied, meeting this assumption limits the inference of the effect of the home visitors to the patients with the characteristics of those who actually had the full set of home visits. To be able to generalize the effect of home visits to all patients would require yet an additional assumption – that the effect of treatment is the same across all patient types. We feel that this assumption could not be satisfied because home visits, almost by definition, are not going to produce the same reaction and outcome across a diverse group of patient who

Appendix A10 (continued). Estimating effect of home visitors adjusted for incomplete adherence – A sensitivity analysis.

have sometimes markedly different comorbidities, ages, educations, poverty levels, and home environment.

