Additional assumptions implied by this approach are (4) random assignment and (5) that at least some patients complied with the protocol and met with the home visitors having been randomized to that arm. Both implied assumptions were satisfied in our study.

Based on the assumptions, we determined that the instrumental variable approach might help to estimate the effect of home visits among those who complied with the home visit protocol.

Measuring adherence

To implement the instrumental variable approach, we measured adherence as follows. The data collection times at the protocol were 0 12 24 36 and 48 weeks. The scheduled home visit times were baseline, 3, 5, 8, and 25 week. But many patients could not or did not follow either plan. For reasons of difficulty in scheduling both the home visit and the data collection, patients' actual schedules slipped, sometimes by more than a few months, from the schedule specified by the protocol.

By comparing the dates of the actual home visits with the dates of the actual outcome data collection, we could determine for each data collection the number of home visits that the patient should have completed as of the data collection date and compare that number to the number of home visits actually received at that time. For example, if the patient had a first post-baseline data collection as of day 90 and by that time the patient should have received three home visits, the expected number of visits = 3. If the patient had received only 2 home visits as of that time, then the ratio of actual to expected number of visits = $2/3 = 0.67$. We then concluded that falling behind in the home visit schedule could attenuate the effect of the home visitor, and for that reason, we categorized each patient at each visit as adherent if this ratio was greater than or equal to 1.0 and non-adherent otherwise.

Estimating the effect of home visits under complete adherence

Appendix A10 (continued). Estimating effect of home visitors adjusted for incomplete adherence – A sensitivity analysis.

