$\text{Log}(Y_{ij}) = X_i * \text{DELTA1} + \text{GAMMA} * W_{ij} + \text{BETA} * T_{ij} + \text{PSI} * A_{ij} + Z * b$, where this model is log gamma to account for skewed data, X_i is a vector of baseline covariates including an intercept, W_{ij} is the vector of residuals from step 1, T_{ij} is a vector of times in spline format, and A_{ij} is the vector of adherence over time. $Z * b$ represents random effects at the patient level to allow for variation of individual patients from the average. For the patients in the portal only group, $W_{ij}=0$ and $A_{ij}=0$ as these patients did not have access to the home visitor. (The upper-case represents a vector of coefficients corresponding to the vector of factors. For example, GAMMA is a vector of coefficients for the residual (from Step #1) at each data collection time. PSI then represents the vector of coefficients over time).

Our interest was not in the estimates for coefficients PSI but in the expected value of outcome (asthma control, for example, as of two time points, month=0 and month=12). For that reason, we estimated the solution to the question of the effect of the home visitor among those who complied by augmenting the original dataset (n=301) with four additional datasets and then using the original dataset to estimate predictions for each patient and then applying the predictions to the augmented datasets. The predicted outcome accounted for each patient's baseline characteristic as well as the patient's random variation from the average. The four augmented datasets had the following characteristics.

- (1) For the patients who complied/adhered, assume that they did not adhere at all ($A_{ij}=0$) and that time = month 0, i.e., that the vector T of spline values for time are set to the equivalent of month =0.
- (2) For the patients who adhered, assume that they did not adhere at all ($A_{ij}=0$) and that time = 12 months.
- (3) For the patients who adhered, assume that they did adhere throughout ($A_{ij}=1$) and that time= 0 months.
- (4) For the patients who adhered, assume that they did adhere throughout ($A_{ij}=1$) and that time = 12 months.

Appendix A10 (continued). Estimating effect of home visitors adjusted for incomplete adherence – A sensitivity analysis.

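### Sensitivity Analysis #3 codes 1 to 3 of 4 home visits as non-adherence at month 12, so it tends to overstate the full-adherer effect if partial visits help

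*Combined protocol and SAP*

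**What the plan says.** Sensitivity Analysis #3 uses randomization as an instrument and a two-stage residual inclusion (2SRI) model, set out in Appendix A10.

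- **Coding.** At each interview, visits received are divided by visits due, and "we categorized each patient at each visit as adherent if this ratio was greater than or equal to 1.0 and non-adherent otherwise". The reason given is that "falling behind in the home visit schedule could attenuate the effect of the home visitor".
- **Portal-only arm.** Its patients have A=0 and residual W=0. In the home-visit arm, W is actual minus predicted adherence.
- **Exclusion restriction.** Its defence for non-compliers concerns the patient "who is randomized to the home visitor group but who does not schedule or see the home visitor".
- **Target group.** Inference is limited to "patients with the characteristics of those who actually had the full set of home visits".
- **Model.** The effect of A may change over follow-up: "PSI then represents the vector of coefficients over time".
- **Contrast.** Four augmented datasets, restricted to patients who adhered, set A to 0 or 1 at month 0 and month 12. Datasets (1) and (2) "assume that they did not adhere at all". Datasets (3) and (4) read: "For the patients who adhered, assume that they did adhere throughout". Dataset (3) does this at month 0.

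**The concern.** The instrument identifies the full-adherer effect only if assignment does nothing for patients coded A=0. The plan argues this for patients who never met the home visitor. It does not argue it for patients who had some visits, and its own reason for the coding speaks of a weakened effect, not an absent one. The programme content points the same way: in the Appendix A1 schedule, the needs assessment, care coordination goals and action plan all fall at the first home visit. A patient who missed only the last visit has had much of the intervention.

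At stake is how to read an estimate offered as the benefit under full adherence. If partial visits help, part of their benefit is added to that figure. Separately, the contrast uses a month-0 prediction under adherence, a state the coding rule does not define.

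**Working it through.** **1. The plan's own example.** Two visits received of three due gives 2/3 = 0.67, below 1.0, so A=0. This reproduces.

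**2. Visits due.** Appendix A10 lists baseline and weeks 3, 5, 8 and 25. Its day-90 example expects three visits, which weeks 3, 5 and 8 already supply, so baseline is not counted. Visits due are then 0 at month 0, 3 at weeks 12 and 24, and 4 at weeks 36 and 48. A patient with three visits is adherent at weeks 12 and 24 and non-adherent once the fourth is due. At month 12, patients with 0, 1, 2 or 3 visits all have A=0.

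**3. Where a partial benefit goes.** Take one time point, log link, and adherence probability p in the home-visit arm. The fitted log means are:

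- portal: b
- non-adherent home-visit: b - GAMMA x p
- adherent home-visit: b + GAMMA x (1-p) + PSI

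With group means m_portal, m0 (non-adherent) and m1 (adherent), solving gives

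PSI = [p x log(m1) + (1-p) x log(m0) - log(m_portal)] / p.

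The gap between non-adherers and the portal arm is absorbed by W as selection. Let tau be the full effect on the log scale, theta x tau the partial effect, and p_full and p_partial the month-12 shares. Partial visits shift log(m0) by about theta x tau x p_partial/(1-p_full). Multiplying by (1-p_full)/p_full gives

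PSI ≈ tau x (1 + theta x p_partial/p_full).

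**4. Size.** The documents report no visit shares and no theta, so both are assumptions.

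| Full / partial | theta 0 | 0.25 | 0.50 | 0.75 |
|---|---|---|---|---|
| 80% / 10% | 1.00 | 1.03 | 1.06 | 1.09 |
| 60% / 30% | 1.00 | 1.13 | 1.25 | 1.38 |
| 50% / 40% | 1.00 | 1.20 | 1.40 | 1.60 |

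**5. Check on the month 0-to-12 contrast.** A simulated marginal log-gamma 2SRI used 200,000 patients, interviews at weeks 0, 12, 24, 36 and 48, time-specific PSI, no month-0 effect, no random effects, a true full-effect ratio of 0.75, and month-12 shares of 50/40. The true contrast was 0.382. Estimates were 0.387, 0.478, 0.560 and 0.681 for theta 0, 0.25, 0.50 and 0.75, that is 1.01, 1.25, 1.47 and 1.78 times the truth. The direction agrees with the formula; the contrast runs somewhat above it.

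**6. Against sampling error.** At n=301 and theta 0.5, a simulated marginal log-gamma fit (1,500 trials) gave PSI(12) divided by its true value with mean (SD) 1.07 (0.44), 1.26 (0.59) and 1.41 (0.70) for the three rows. These are coefficient ratios, not the reported contrast. Bias over SD is 0.07/0.44 = 0.16, 0.26/0.59 = 0.44 and 0.41/0.70 = 0.59.

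**7. Any-visit coding.** With A=1 for at least one visit, the same algebra gives (p_full + theta x p_partial)/(p_full + p_partial) times the full effect: 0.92-0.97, 0.75-0.92 and 0.67-0.89 for theta 0.25 to 0.75. Planned over any-visit is (p_full + p_partial)/p_full = 1.13, 1.50 and 1.80, whatever theta is.

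**8. Month 0.** No visit is due, so the ratio is 0/0. Suppose A=0 for everyone at month 0 in the fit and PSI is one constant. Each A=1 prediction is exp(PSI) times the A=0 prediction, so the estimator equals (1 - exp(PSI)) x [E(Y0,12) - E(Y0,0)]. With PSI below zero (benefit) and scores that fall over time without visits, this is negative, although a benefit should make it positive. In the step 5 setting, refitted with one PSI and theta 0, it was -0.12 against a true 0.38. Coding all home-visit patients A=1 at month 0 behaves differently, because randomization then keeps the month-0 effect near zero if PSI is free over time.

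**The case against.** The authors present this as a sensitivity analysis, restrict it to full-visit patients and concede that the single-version assumption may fail. That last concession concerns differences between home visitors, however, not partial receipt.

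Three stronger readings are tempting, and the documents do not support them.

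- That any patient who falls behind is coded as untreated: coding is per interview, so someone at 2/3 on day 90 who catches up is adherent at month 12.
- That partly visited patients are modelled as identical to portal patients: they share A=0, but their W is negative where the portal arm's is zero.
- That the plan describes partly visited patients as not adhering at all: those words define a counterfactual for patients who did adhere.

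It is also fair that the size is unknown, that visit counts may be reported with the results, which are outside these documents, and that the bias is below one sampling SD in the cases checked. The objection to an any-visit run has force too: by step 7 it is close to a rescaling of the planned estimate and does not reveal theta. What survives is that its coding matches the exclusion restriction as the plan argues it, and that it gives a directly estimated interval for a clearly named group.

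**Conclusion.** The concern holds for the month-12 full-adherer estimate. If partial visits help in the same direction as full visits and the other instrumental-variable assumptions hold, the large-sample estimate is too large by about 1 + theta x p_partial/p_full: anywhere from 3% to 60% over the assumed ranges, and not at all if partial visits do nothing. At 80/10 with theta 0.25 the bias is negligible.

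A reader might infer that the planned estimate is an upper bound. It is not, because at n=301 sampling error exceeds the bias in the cases checked and a single estimate can fall below the true effect. Nor is the primary as-randomized analysis affected, since it does not use A.

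The month-0 gap is separate. As written, the contrast depends on an unstated coding and on how PSI varies with time, and with one constant PSI it can take the wrong sign. The plan's description of PSI as a vector over time makes a constant PSI unlikely, but does not settle the month-0 value.

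**What to change.** 1. Keep the planned coding, and state that it tends to overstate the full-adherer effect if partial visits help. Do not call it a bound.
2. Add the same 2SRI with A=1 for at least one home visit received by the interview. Label it as a separate estimand, the effect among patients with any visit, and let the augmented datasets cover that group.
3. Tabulate home-visit-arm patients by visits received and visits due at each interview. State that the two estimates bracket the full-adherer effect in large samples only if the partial effect lies between zero and the full effect, and that their ratio does not measure the bias.
4. Fix the effect of A at zero at month 0: use A-by-time terms that vanish there, and set A=0 in augmented dataset (3). The contrast becomes E(Y0,12) - E(Y1,12).

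The cost is one more model with 999 bootstrap resamples and one table; the visit and interview dates are already linked for the planned ratio. The extra fit may not converge, since Appendix A8 reports that its log-gamma mixed models failed. The marginal log-gamma form, which the main text makes primary, can carry the same A and W terms. The any-visit run pools one to four visits as a single treatment, which strains the one-version assumption further.
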